### **Safety Analyses**

N/A

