### **Known Potential Risks**

Primary risks of the study include: a) embarrassment or discomfort with study questions; b) emotional, social, or physical harms resulting from the suggested behavioral modifications; c) inadvertent disclosure of data; d) Inadequacy of informed consent; or e) other risks that are unlikely to occur, but could. We discuss below methods to protect against these risks:

Embarrassment or discomfort with detailed behavioral questions or institutional structure can occur. This risk is minimized by ensuring that participants know they do not have to participate or may only answer the questions that they feel comfortable answering. We will refer patients to seek care from their regular medical doctor in the event the participant experiences any emotional or physical discomfort or will remind them that they can stop participation in the study at any point in time.

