**PROTOCOL TITLE: Testing mHealth Delivery of Cognitive Behavioral Therapy for Insomnia to Breast Cancer Survivors**

**17.1**

Data collection will be the responsibility of the MHRI trial staff at the site under [name] supervision. All data will be stored within MHRI's secure REDCap system. [name] will be responsible for ensuring the accuracy, completeness, legibility, and timeliness of the data reported, as well as for storing all informed consent documents and for managing any other identifiable information, including any audio recordings or transcripts.

All study data will be collected in REDCap and non-PHI will be downloaded into a SAS dataset. Study documents will be retained for a minimum of 3 years after the last annual Federal Financial Report (FFR) is submitted. Data will be stored behind the MedStar Health firewall in Box.

Clinical data (including adverse events (AEs), concomitant medications, and expected adverse reactions data) will be entered into REDCap, a 21 CFR Part 11-compliant data capture system provided by the Medstar Health Research Institute. The data system includes password protection and internal quality checks, such as automatic range checks, to identify data that appear inconsistent, incomplete, or inaccurate. While participants will be recruited from multiple sites, all records will be collected and stored by MHRI and only MHRI research staff who have a need will be able to see identifiable information.

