### Time Period and Frequency for Event Assessment and Follow-Up

We do not anticipate adverse event (AE) or serious adverse event (SAE) during the course of this study. However, the principal investigator will be responsible for following adverse event reporting requirements as outlined below. These responsibilities include:

- a. Reviewing the accuracy and completeness of all adverse events reported
- b. Compliance with IRB policies for reporting adverse events and/or serious adverse events
- c. Closely monitoring research participants at each point of contact for any new Adverse Events (AEs) or Serious Adverse Events (SAEs).

All AEs, not otherwise precluded per the protocol, will be captured on the appropriate case report form (CRF). Information to be collected includes event description, time of onset, assessment of severity, relationship to study procedures, and time of resolution/stabilization of the event. All AEs occurring while on study will be documented appropriately regardless of relationship. All AEs will be followed to adequate resolution.

Any medical or psychiatric condition that is present at the time that the participant is screened will be considered as baseline and not reported as an AE. However, if the study participant's condition deteriorates at any time during the study, it will be recorded as an AE. Changes in the severity of an AE will be documented to allow an assessment of the duration of the event at each level of severity to be performed.

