### Serious Adverse Event Reporting

1. The study is of low to moderate risk. No serious adverse events are expected.

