**PROTOCOL TITLE: Testing mHealth Delivery of Cognitive Behavioral Therapy for Insomnia to Breast Cancer Survivors**

2. We will attempt to report serious unanticipated events within 24 hours to the GU/MHRI IRB, but no longer than 3 business days. Adverse events will be considered serious if graded 3 or higher on the scale outlined above.
3. An adverse event report including a description of the event, when the event occurred, and when and how the event was reported, will be generated for each event. Any documentation related to the event or its attribution will be included in the report.
4. The study PI point of contact with the IRB ([name]) will conduct a review of all adverse events upon completion of every study subject. She will evaluate the frequency and severity of the adverse event(s) and, in conjunction with the IRB at GU/MHRI, will determine if modifications to the protocol or consent forms are required.

The IRB will evaluate whether the study should continue unchanged, require modification, continue, or close to enrollment. If increased frequency of serious adverse events is detected and reported, an ad hoc safety review will be convened to determine whether and how to modify, continue, or terminate enrollment.

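### Safety analyses are set to N/A although every adverse event is recorded: no by-arm summary is prespecified, the SAE review has no stated reference, and the risk labels conflict

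*Combined protocol and SAP*

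**What the plan says.** Section 17.0 gives no safety analysis; the heading and its content read "Safety Analyses N/A". Planned interim analyses are also N/A.

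Elsewhere the protocol builds a full AE system:

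- **Foreseen harm.** Section 15.0 (Known Potential Risks) counts among the primary risks "emotional, social, or physical harms resulting from the suggested behavioral modifications".
- **Capture.** Section 18.0 (Time Period and Frequency for Event Assessment and Follow-Up) states that "All AEs occurring while on study will be documented appropriately regardless of relationship". Description, onset, severity, relationship and resolution are recorded for each event.
- **Storage.** Section 17.1: "Clinical data (including adverse events (AEs), concomitant medications, and expected adverse reactions data) will be entered into REDCap".
- **Review.** Section 18.0 (Serious Adverse Event Reporting) has the PI assess AE frequency and severity after each participant finishes, and adds: "If increased frequency of serious adverse events is detected and reported, an ad hoc safety review will be convened".
- **Risk level.** Section 18.0 opens by declaring monitoring provisions N/A because the research is only minimal risk; sections 15.0 and 20.0 use the same label. Under Serious Adverse Event Reporting the text is "The study is of low to moderate risk. No serious adverse events are expected".

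**The concern.** One component of the program limits time in bed to the user's average total sleep time (section 3.0, Sleep restriction). Controls receive a website with educational content only (section 5.0). Breast cancer survivors can be expected to have background medical events whichever arm they are in. The randomised control arm is the natural means of telling program-related events from background events, and the protocol requires the data for that comparison. With safety analyses set to N/A, which AE summaries are shown, in what categories and with what denominators, is left to be decided after the data are seen.

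The ad hoc review raises a second question: a frequency can be called increased only relative to something, and the text names nothing. The third is that the documents disagree about how risky the study is, which bears on how much safety analysis is proportionate.

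**Working it through.** **1. Is a by-arm AE summary prespecified anywhere?** The plan states no safety figure, so this step is a reading.

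- Section 17.0, Safety Analyses: N/A.
- Section 17.0, primary and secondary analyses: ISI, sleep-diary measures, and PROMIS fatigue and depression by arm. These are symptom scores, not AEs.
- Section 17.0, General Approach: CONSORT is to be followed. Section 8.0: results go to the trial registry. Neither mentions AEs by arm.
- Section 18.0: reviews of AE frequency and severity, with no reference to arm.

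No section commits to AE counts by arm.

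**2. What is the SAE review measured against?** The rule gives no reference rate, threshold, time window or arm. The Expectedness paragraph judges frequency against risk information already described, but section 15.0 lists risks without rates. The only candidate is the statement that no SAEs are expected.

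If that means zero, one background SAE would count as an increase. The documents give no background rate, so p is an assumption and a range is shown. The chance of at least one SAE is 1 − (1 − p)^n. Arm size is 76/2 = 38, and the probability of no SAE among all 76 women is the square of that for 38.

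| Assumed SAE rate over the study | n = 38 (one arm) | n = 76 (pooled) |
|---|---|---|
| 1% | 32% | 1 − 0.683² = 53% |
| 2% | 54% | 1 − 0.464² = 78% |
| 5% | 86% | 1 − 0.142² = 98% |
| 10% | 98% | 1 − 0.018² > 99% |

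Read as more than zero, the rule would probably fire on background events alone unless the rate is below about 1%. On any other reading the reference still has to be supplied.

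The event to be counted is also unclear. Serious Adverse Event Reporting calls events serious from grade 3 upward on the severity scale above it. That scale has no numeric grades, and it warns that severe and serious are not the same.

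**3. What could a by-arm table show at 38 per arm?**

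- Zero events in one arm, exact upper 95% limit: two-sided 1 − 0.025^(1/38) = 9.3%; one-sided 1 − 0.05^(1/38) = 7.6%.
- 0/38 against 0/38: Newcombe 95% CI for the difference, about −9.2 to +9.2 percentage points.
- Fisher exact test, two-sided: 5 against 0 gives p = 0.054; 6 against 0 gives p = 0.025.

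Counts with intervals are informative to that extent; a significance test would have little power. These limits follow from the sample size and do not measure the size of the defect.

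**4. Would the arms be observed equally?** Section 18.0 has AEs looked for whenever staff are in contact with a participant. Section 5.0 describes staff outreach after device delivery and technical support through the app for the intervention arm, and no matching contacts for controls. Both arms complete post-intervention forms at six weeks (section 6.0). A raw count could therefore be higher in the intervention arm because more events are found there.

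**The case against.** The strongest defence is that this is a small, low-risk behavioural trial with safeguards working event by event. Section 18.0 requires a report for every event, clinician assessment of causality, prompt IRB notification of serious unanticipated events, and PI review with the IRB after each participant finishes. CONSORT and registry reporting leave room for an AE table. A table at 38 per arm would resolve little.

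Much of this stands, and it rules out several stronger readings that a reader might infer:

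- **That the trial can say nothing about harm.** The documents do not support this. Total sleep time, sleep efficiency, sleep quality, and PROMIS fatigue and depression are to be examined by arm, and these bear on the effect of cutting time in bed. The ISI comparison would show average worsening.
- **That the review cannot work without by-arm counts.** Individual reports or pooled counts can prompt it. The rule is imprecise, not inoperable.
- **That safety analyses are N/A because the study is minimal risk.** Section 17.0 gives no reason. The minimal-risk N/A heads a different section, 18.0, on monitoring.
- **That section 16.0 asserts a favourable benefit-risk result from the trial.** It is a prospective statement made to justify the study.

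What the defence does not answer is that none of these provisions prespecifies an AE summary by arm, names a reference for the review, or reconciles the risk wording.

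**Conclusion.** The point holds in limited form. AEs must be recorded in full and harm from the behavioural advice is a named risk, yet safety analyses are declared N/A, so no by-arm AE summary is prespecified. The SAE review lacks a stated reference. Minimal risk in sections 15.0, 18.0 and 20.0 conflicts with low to moderate risk under Serious Adverse Event Reporting.

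The importance is moderate: the plan should be changed, but the primary analysis, the sample size of 76 and the efficacy conclusion do not depend on it. What is lost is a prespecified comparison that could bound harm only loosely, at 9.3% for zero events in 38 women. That limit assumes 38 women in the arm, all observed for AEs. The probabilities for the review rest on assumed SAE rates of 1% to 10%, because the documents give none.

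**What to change.** 1. **Replace N/A in section 17.0, Safety Analyses,** with a descriptive table by randomised arm, with all randomised women as denominator. Give the number and percent with any AE, any severe AE, any SAE, any AE judged at least potentially related, and any AE leading to discontinuation. Add exact 95% confidence intervals and no significance test.
2. **Add the number of women whose ISI score is worse at week 6 than at baseline,** by arm, among those with post-intervention data. Similar PROMIS counts are not proposed, because section 6.0 does not make clear when PROMIS is administered.
3. **Base the by-arm comparison on AEs ascertained the same way in both arms,** for example at the common post-intervention contact, and show how many women reached it. Otherwise state that the intervention arm's extra contacts may inflate its count.
4. **Have the investigators state what an increased SAE frequency is measured against** in section 18.0, and reconcile the two statements of what makes an event serious. The choice is theirs; ongoing by-arm review is not required, since that would change the monitoring procedure.
5. **Reconcile the risk wording** in sections 15.0, 18.0 and 20.0.

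The cost is one extra table with wide intervals and some rewording. The documents do not say that the post-intervention forms ask about AEs; if they do not, the common-contact option in item 3 adds a short question to them. The sample size and the primary analysis do not change.

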### **Baseline Descriptive Statistics**

We will compare intervention and control arms on baseline characteristics using means for continuous variables (age) and frequencies for categorical variables (e.g. stage, education, race/ethnicity, marriage status, employment). Variables such as time since diagnosis or level of physical activity may be analyzed as continuous or categorical depending on the distribution of the data. As recommended by CONSORT guidelines, we will not calculate baseline statistically significant differences by study arm.

### **Planned Interim Analyses**

N/A

### **Sub-Group Analyses**

We will explore data by participant age, race, and recruitment site, if we have appropriate numbers. These analyses will be exploratory in nature.

### **Tabulation of Individual Participant Data**

Individual participant data will not be listed by measure and time point. Rather, it will be presented in the aggregate.

**PROTOCOL TITLE: Testing mHealth Delivery of Cognitive Behavioral Therapy for Insomnia to Breast Cancer Survivors**

**17.1**

Data collection will be the responsibility of the MHRI trial staff at the site under [name] supervision. All data will be stored within MHRI's secure REDCap system. [name] will be responsible for ensuring the accuracy, completeness, legibility, and timeliness of the data reported, as well as for storing all informed consent documents and for managing any other identifiable information, including any audio recordings or transcripts.

All study data will be collected in REDCap and non-PHI will be downloaded into a SAS dataset. Study documents will be retained for a minimum of 3 years after the last annual Federal Financial Report (FFR) is submitted. Data will be stored behind the MedStar Health firewall in Box.

Clinical data (including adverse events (AEs), concomitant medications, and expected adverse reactions data) will be entered into REDCap, a 21 CFR Part 11-compliant data capture system provided by the Medstar Health Research Institute. The data system includes password protection and internal quality checks, such as automatic range checks, to identify data that appear inconsistent, incomplete, or inaccurate. While participants will be recruited from multiple sites, all records will be collected and stored by MHRI and only MHRI research staff who have a need will be able to see identifiable information.

**18.0 Provisions to Monitor the Data to Ensure the Safety of Subjects\***

*N/A. This research involves only Minimal Risk to subjects.*

[name] will have primary responsibility for monitoring the data and safety of this project and complying with the reporting requirements of the funding agency and the IRB of record (MHRI IRB). As part of the annual progress report to the NIH sponsor, the PI will provide an update of project activities to date, summary of the characteristics of participants, expected versus actual enrollment, and any changes to the protocol. The PI will work closely with members of the study team to ensure that a quality assurance plan and the data and safety monitoring plan are thoroughly followed.

**Adverse events and Serious Adverse Events**

**Definition of Adverse Events**

This protocol uses the definition of adverse event from 21 CFR 312.32 (a): any untoward medical occurrence associated with the use of an intervention in humans, ***whether or not considered intervention-related.***

**Definition of Serious Adverse Events**

A serious adverse event (SAE) is any untoward medical occurrence that:

- Results in death.
- Is life-threatening. Any adverse experience that places the subject, in the view of the investigator, at immediate risk of death from the reaction as it occurred (i.e., it does not include a reaction that, had it occurred in a more serious form, might have caused death).

## PROTOCOL TITLE: Testing mHealth Delivery of Cognitive Behavioral Therapy for Insomnia to Breast Cancer Survivors

- Requires in-patient hospitalization or prolongation of existing hospitalization.
- Results in persistent or significant disability or incapacity.
- An event that requires intervention to prevent permanent impairment or damage.
- Important medical events that do not result in death, are not life-threatening, or do not require hospitalization may be considered serious adverse events when, based upon appropriate medical judgment, they might jeopardize the subject and might require medical or surgical intervention to prevent one of the outcomes listed above.

### Classification of an Adverse Event

#### Severity of Event

For adverse events (AEs) not included in the protocol defined grading system, the following guidelines will be used to describe severity.

- **Mild** – Events require minimal or no treatment and do not interfere with the participant's daily activities.
- **Moderate** – Events result in a low level of inconvenience or concern with the therapeutic measures. Moderate events may cause some interference with functioning.
- **Severe** – Events interrupt a participant's usual daily activity and may require systemic drug therapy or other treatment. Severe events are usually potentially life-threatening or incapacitating. Of note, the term "severe" does not necessarily equate to "serious".

### Relationship to Study INTERVENTION/Experimental Manipulation

All adverse events (AEs) will have their relationship to study procedures, including the intervention, assessed by an appropriately-trained clinician based on temporal relationship and his/her clinical judgment. The degree of certainty about causality will be graded using the categories below.

- **Definitely Related** – There is clear evidence to suggest a causal relationship, and other possible contributing factors can be ruled out. The clinical event, including an abnormal laboratory test result, occurs in a plausible time relationship to study procedures administration and cannot be explained by concurrent disease or other drugs or chemicals. The response to withdrawal of the study procedures should be clinically plausible. The event must be pharmacologically or phenomenologically definitive.
- **Probably Related** – There is evidence to suggest a causal relationship, and the influence of other factors is unlikely. The clinical event, including an abnormal laboratory test result, occurs within a reasonable time after administration of the study procedures, is unlikely to be attributed to concurrent disease or other drugs or chemicals, and follows a clinically reasonable response on withdrawal.
- **Potentially Related** – There is some evidence to suggest a causal relationship (e.g., the event occurred within a reasonable time after administration of study procedures). However, other factors may have contributed to the event (e.g., the participant's clinical condition, other concomitant events). Although an AE may rate only as "possibly related" soon after discovery, it can be flagged as requiring more information and later be upgraded to "probably related" or "definitely related", as appropriate.

## PROTOCOL TITLE: Testing mHealth Delivery of Cognitive Behavioral Therapy for Insomnia to Breast Cancer Survivors

- **Unlikely to be related** – A clinical event, including an abnormal laboratory test result, whose temporal relationship to study procedures administration makes a causal relationship improbable (e.g., the event did not occur within a reasonable time after administration of the study procedures) and in which other drugs or chemicals or underlying disease provides plausible explanations (e.g., the participant's clinical condition, other concomitant treatments).
- **Not Related** – The AE is completely independent of study procedures administration, and/or evidence exists that the event is definitely related to another etiology. A clinician will document the alternative, definitive etiology.

### Expectedness

A clinician with appropriate expertise in breast cancer and/or CBT-I will be responsible for determining whether an adverse event (AE) is expected or unexpected. An AE will be considered unexpected if the nature, severity, or frequency of the event is not consistent with the risk information previously described for the study procedures.

### Time Period and Frequency for Event Assessment and Follow-Up

We do not anticipate adverse event (AE) or serious adverse event (SAE) during the course of this study. However, the principal investigator will be responsible for following adverse event reporting requirements as outlined below. These responsibilities include:

- a. Reviewing the accuracy and completeness of all adverse events reported
- b. Compliance with IRB policies for reporting adverse events and/or serious adverse events
- c. Closely monitoring research participants at each point of contact for any new Adverse Events (AEs) or Serious Adverse Events (SAEs).

All AEs, not otherwise precluded per the protocol, will be captured on the appropriate case report form (CRF). Information to be collected includes event description, time of onset, assessment of severity, relationship to study procedures, and time of resolution/stabilization of the event. All AEs occurring while on study will be documented appropriately regardless of relationship. All AEs will be followed to adequate resolution.

Any medical or psychiatric condition that is present at the time that the participant is screened will be considered as baseline and not reported as an AE. However, if the study participant's condition deteriorates at any time during the study, it will be recorded as an AE. Changes in the severity of an AE will be documented to allow an assessment of the duration of the event at each level of severity to be performed.

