**5.0 Study Intervention/Investigational Agent**

**Intervention Condition.**

After randomization to the intervention arm participants will receive an Amazon Echo Dot with the Sleep Helper skill and will be asked to enroll either by giving responses to voice prompts for setup or entering baseline information via an accompanying smart phone application. Participants will receive written instructions for how to enroll. The MHRI research team will reach out to participants by email and/or phone after delivery confirmation to ensure that participants have enrolled and initiated the program. Participants will receive written instructions to complete morning, night, relaxation and educational modules daily. Participants will also be instructed on security settings that will be pre-set for maximal security.

**Intake.** At the start of the intervention participants will be provided with written instructions on setting the program up and asked to complete an intake form on background information, which can be completed via the smart phone app. Participants will be able to use a smart phone app to enter standard insomnia intake assessment information that includes sleeping patterns, sleep hygiene practices (e.g. timing and

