## PROTOCOL TITLE: Testing mHealth Delivery of Cognitive Behavioral Therapy for Insomnia to Breast Cancer Survivors

frequency of caffeine use of screens, primary meals and exercise, etc.), whether they have a bed partner, and general background information for the study. The smart phone app will be linked with the smart speaker device so that information added in any format enters the same user backend database.

Participants will be encouraged to complete the morning and night modules daily, and to listen to relaxation and educational content or review written educational content on the accompanying smart phone app. Media Rez will maintain a technical support system through the app for user difficulties and will track all inquiries using de-identified participant ID numbers. App support rather than phone support will be utilized to maintain participant privacy so that phone numbers will not be revealed. The morning module collects sleep diary data from the preceding night and provides participant specific reminders based on participant data on naps, exercise and other daily activities. The morning module also walks the user through the sleep schedule (e.g., recommended sleep bedtime schedule based on sleep restriction algorithm and participant specific bedtime routine guidance), questions about intake of caffeine and nicotine, napping, and exercise (data collection), and automated control of lighting to facilitate preparation for sleep. Educational programming includes short sleep education content and cognitive restructuring. The evening module gathers data regarding productivity, tiredness, and mood from that current day. The relaxation modules are prompted upon completion of the night module, although users are able to request a relaxation exercise at any point in time.

**Control Condition.** Controls will have access to a website with information about CBT-I and breast cancer survivorship and will be told to engage with the website as desired. The content will be drawn from the same education script that is programmed into the Alexa device.

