**Data collection.** Baseline data before randomization will be collected from all participants using REDCap. We will have a separate link to a password protected recruitment document (with name and contact information) where unique study IDs will be assigned, thus further protecting the identity of participants. In the de-identified REDCap forms we will collect information on basic demographics (e.g. age, race/ethnicity, body mass index, education, marital status), medical history (e.g. comorbidities, time since treatment), and lifestyle habits (e.g. physical activity, alcohol consumption) as well as our primary outcome of the Insomnia Severity Index (ISI). Before randomization and upon completion of the intervention and control, participants will be administered surveys of relevant questions from the CSD through REDCap. We will collect basic sleep information including time getting into bed, time attempting to go sleep, time awake during the night, time awake in the morning, time getting out of bed, number of awakenings, and quality of sleep. We will also collect information on the PROMIS 29-item scale to see how co-occurring symptoms such as fatigue and anxiety are distributed by group. Additional information to be collected includes a morning/eveningness questionnaire to assess chronotype and participant expectations and motivations. All data will be self-reported.

Ongoing data collected through the Alexa app includes basic sleep information including time getting into bed, time attempting to go sleep, time awake during the night, time awake in the morning, time getting out of bed, number of awakenings, and quality of sleep. The ongoing data collected is used to inform treatment recommendations, but is not considered in the primary or secondary outcome analyses, which are based on the ISI and CSD.

Upon completion of the program, participants in the intervention arm will complete a system usability scale as well as a set of open-ended feedback questions after completion of the other REDCap forms.

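### Adverse events are sought at points of contact that differ by arm, and health complaints made to app support have no described route to the investigator

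*Combined protocol and SAP*

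**What the plan says.** Section 18.0 (Time Period and Frequency for Event Assessment and Follow-Up) sets a broad aim: "All AEs occurring while on study will be documented appropriately regardless of relationship". Among the investigator's responsibilities it lists "Closely monitoring research participants at each point of contact for any new Adverse Events (AEs) or Serious Adverse Events (SAEs". It also counts deterioration of a condition present at screening as an AE.

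Section 5.0 describes the contacts. Under Intervention Condition: "The MHRI research team will reach out to participants by email and/or phone after delivery confirmation", to check that the program has been started. Under Intake: "Media Rez will maintain a technical support system through the app for user difficulties and will track all inquiries using de-identified participant ID numbers". Under Control Condition, women are given a website to use as they wish, and nothing further is scheduled.

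Section 6.0 (Data collection) has both arms complete REDCap forms before randomization and at the end. Only at the end, and only in one arm, "participants in the intervention arm will complete a system usability scale as well as a set of open-ended feedback questions". Section 14.0 records reasons when a woman stops using the Sleep Helper skill and asks her to complete the post-intervention assessments anyway. Section 17.0 marks Safety Analyses N/A.

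**The concern.** When events are picked up at contacts, the number recorded depends on how often and how openly women are asked. If one arm has more contacts, its count can be higher with no difference in what happened to the women.

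This matters here for two reasons. Section 15.0 names emotional, social or physical harm from the behavioral changes as a risk, and judging such harm calls for a comparable control rate. AE frequency is also used in decisions. Under Expectedness in Section 18.0, frequency helps decide whether an event is unexpected. Under Serious Adverse Event Reporting, the investigator weighs frequency and severity when considering changes to the protocol or consent forms, and a rise in serious events triggers an ad hoc review.

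A second, separate gap concerns participant protection: a health complaint typed into app support reaches the developer, and the text stops there.

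**Working it through.** The plan gives no figure to reproduce on this point, so the check sets the sections side by side.

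**1. How events are found.** Section 18.0 describes monitoring at contacts. Its case report form fields, and the REDCap entry of AEs in Section 17.1, cover recording an event already known. The investigator's review as each woman completes (Serious Adverse Event Reporting) covers events already reported. No AE questionnaire, checklist or scheduled AE call is described for either arm.

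**2. Contacts by arm.**
- Intervention only: post-delivery email or phone outreach (5.0); recorded reasons for stopping the skill (14.0); open-ended feedback questions (6.0). Daily modules also collect tiredness and mood (5.0), but no rule turns an entry into an AE.
- Control only: none.
- Both arms: baseline and six-week forms (6.0); the reason recorded if a woman withdraws from the study (14.0); up to 5 calls or emails to those who do not return forms (14.0). The described form content includes the ISI, sleep diary items, PROMIS-29, chronotype, and expectations and motivations. No AE question is described.

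**3. App support.** Section 5.0 tells the developer to track inquiries. Section 19.0 has it pass de-identified data to MHRI for analysis. Neither says that a health complaint goes to the investigator. Section 18.0 requires mild to moderate events to reach the IRB within 5 business days, and serious unanticipated events within 24 hours if possible and 3 business days at most.

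**4. Illustration of the mechanism (assumed inputs, not an estimate).** From Section 17.0: 38 women per arm. Assumed: a true AE rate of 20% in both arms; a chance q of 0.2 to 0.5 that any one contact reveals an event; one effective contact for controls; two or three for the intervention arm. App support is left out, because a complaint that is never forwarded adds nothing to the count.

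Detection over k contacts is 1 − (1 − q)^k. Expected recorded events are 38 × 0.20 × detection = 7.6 × detection.
- Control, k = 1: 7.6 × 0.2 = 1.5; 7.6 × 0.5 = 3.8.
- Intervention, k = 2: 7.6 × 0.36 = 2.7; 7.6 × 0.75 = 5.7. Ratios to control: 0.36/0.2 = 1.8 and 0.75/0.5 = 1.5.
- Intervention, k = 3: 7.6 × 0.488 = 3.7; 7.6 × 0.875 = 6.65. Ratios: 0.488/0.2 = 2.44 and 0.875/0.5 = 1.75.

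The true ratio is 1.0 throughout. If the extra contacts reveal nothing, the recorded ratio is also 1.0. The ratio does not depend on the assumed 20%.

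**The case against.** Much of the case on the other side stands.

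- **No comparison is planned.** Safety Analyses are N/A and Section 18.0 rates the study minimal risk. A reader might infer that a trial result is biased. The documents do not support that: the imbalance touches only by-arm counts that may be reported and the frequency reviews in Section 18.0.
- **Silence is not proof.** The monitoring duty is one item in a list that is not said to be complete, a separate data and safety monitoring plan is mentioned, and the forms are not reproduced. A reader might infer that controls have almost no way to have an event recorded. The text shows only that no other method is described, and the duty to monitor covers all participants.
- **The extra routes are weak.** The outreach falls at set-up, when exposure is small, and the open-ended questions ask for program feedback. App support cannot both inflate the intervention count and fail to reach the investigator; only the second point is made here.
- **Some comparison exists.** ISI is collected in both arms, and PROMIS-29 fatigue and depression are to be explored by arm. A reader might infer that harm cannot be judged against control at all. That goes too far, although these scores do not cover accidents, injuries or other events, and no rule converts a score change into an AE.
- **Reporting clocks.** A reader might infer that the IRB time limits start when the investigator becomes aware. No section says what starts them. The narrower point stands: a complaint that never reaches the investigator may go unreported.

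The objection does not remove the mismatch between the promise to document all events in both arms and contacts described mainly for one.

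**Conclusion.** The point holds as a cheap improvement, not as a flaw in any planned analysis. As described, AE detection is unequal between arms. By-arm AE counts would therefore not be comparable, the frequency reviewed under Section 18.0 would mix event rate with opportunity to report, and events in controls are likely to be under-recorded. This rests on taking the described contacts as the actual ones.

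The size is unknown. The illustration gives recorded ratios of 1.5 to 2.4 with no true difference, and 1.0 if the extra contacts reveal nothing. A reader might take a doubling as the expected effect, but the documents give no AE rate and no detection rate to support any particular value.

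The missing route from app support to the investigator is a separate gap that concerns individual protection and reporting rather than the comparison of arms.

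**What to change.** 1. In Section 6.0, add one identical AE question to the six-week REDCap form in both arms: any new or worsened health problem, accident or injury over the six weeks, with onset date and care sought. Women who stop the program are already asked to complete the post-intervention assessments under Section 14.0, so no extra mailing is needed. State that any tabulation of AEs by arm rests on this item alone.
2. In Section 5.0, state that the developer promptly forwards to the MHRI investigator, by study ID, any app-support inquiry that describes a health complaint. These reports serve participant protection and IRB reporting, and stay out of any by-arm tabulation.

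The cost is one form item, one sentence on forwarding and a little participant time. More AEs will be recorded, which adds some reporting work.
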